2.2 Primary endpoints

The primary endpoints are:

- The change in PCWP at each pacing frequency (+20 bpm, +40 bpm, +60 bpm) with its corresponding optimal AV delay at rest, compared to PCWP at the intrinsic heart rate.
- The change in PCWP at each pacing frequency (+10 bpm, +30 bpm, +50 bpm) using dynamic AV delay programming, while avoiding truncation, compared to PCWP at the intrinsic heart rate during exercise (cycle ergometry at 10 and 25 Watts)

The PCWP at the intrinsic heart rate is defined as the average of the PCWP at the intrinsic heart rate heart rate before and after each pacing step.

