3.2 Exclusion criteria

Participants eligible for this Study must **not** meet any of the following criteria:

1. Participant has a history of:
 - a. Evidence of significant pulmonary comorbidity based on abnormal pulmonary function tests (FEV1 <60%) or aberrant lung parenchyma more than mild on radiological imaging
 - b. Severe/symptomatic valvular diseases
 - c. Severe pulmonary hypertension (PASP > 55mmHg estimated by Doppler Echo)
 - d. Unstable arrhythmias (VT, VF)
 - e. Recurrent syncopes after pacemaker implantation
 - f. Episode of atrial fibrillation in the last 3 months
 - g. Amyloid cardiomyopathy
2. Physical inability to perform exercise
3. More than 1 hospitalization for heart failure in the last year
4. Resting HR > 100bpm
5. At time of iCPET or inclusion: decompensated heart failure, unstable coronary syndrome
6. Contraindication to central venous access
 - a. Severe coagulopathy (e.g., spontaneous INR > 2, thrombocytopenia < 50,000/ μ L)
 - b. Local infection or skin infection at the insertion site
 - c. Thrombosis or anatomical abnormalities of the right jugular vein
 - d. Pneumothorax or contralateral lung pathology
 - e. Inability to properly position the patient
7. Contraindication to arterial access
 - a. Thrombosis or occlusion of the target artery
 - b. Raynaud's phenomenon or other vasospastic disorders
 - c. Active infection at the intended insertion site
 - d. Severe coagulopathy (e.g., spontaneous INR > 2, thrombocytopenia < 50,000/ μ L)
 - e. Insufficient collateral circulation (e.g., inadequate perfusion in an Allen test)
8. Contraindications to CPET
 - a. ECG signifying myocardial injury

- b. ECG signifying current or potentially lethal arrhythmias
- c. Systemic hypotension (e.g. systolic blood pressure < 90 mmHg)
- d. Extreme hypertension (e.g. systolic blood pressure > 220 mmHg)
- e. Syncope, presyncope, or lightheadedness
- f. SaO₂ < 88%
- g. Severely elevated PCWP (> 40 mmHg) during exercise

Participants who meet one or more of the above exclusion criteria **must not proceed** to be enrolled/randomized in the study and will be documented as a screen failure via applicable log forms in Investigator Site File.

4 Study procedures

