4.2.2 Other study assessments & procedures

4.2.2.1 *Study specific and other procedures/investigations:*

Additional procedures needed for screening

All patients known to receive left bundle branch area (LBBa) pacing at the time of ethics committee approval will be screened for eligibility by reviewing their medical records in KWS (n = 274 + n = 400). Eligible patients, based on the already available data, will be approached during their annual consultation.

If they consent to participate in the study, additional information will be collected if not already available:

- Recent transthoracic echocardiography (\leq 3 months), with the following parameters:
 - Ejection fraction
 - Septal e', lateral e', average E/e' or TR velocity
 - If septal e' \geq 7cm/s or lateral e' \geq 10cm/s or TR velocity \leq 2.8 m/s: GLS
 - LAVI or LVMI and RWT
 - If LAVI \leq 34 ml/m² or LVMI $<$ 149/122 g/m² or RWT \leq 0,42: LV wall thickness
 - Doppler echocardiographic estimated pulmonary artery systolic pressure
- Recent blood test with the following (\leq 3 months):
 - Thrombocyte count, INR
 - NT-proBNP
 - HbA1c
- ECG at time of consultation
- Weight and length at time of consultation
- Blood pressure at time of consultation
- NYHA classification at time of consultation

When meeting all eligibility criteria, patients will be contacted to schedule the invasive cardiopulmonary exercise test (iCPET).

The study protocol

Eligible patients will undergo one protocol at rest and two protocols in exercise as described below. The technical setup for iCPET with a cycle ergometer is already available at UZ Leuven and Jessa Hospital (S65913).

First, patients will be welcomed at the catheterization lab and receive a detailed explanation of the study protocol. A brief history taking and clinical examination will assure there are no signs of acute heart failure, nor unstable coronary syndrome. Then blood pressure and peripheral oxygen saturation will be assessed non-invasively. An ECG will be taken and evaluated. If all eligibility criteria are still met, the iCPET will proceed.

The interventional cardiologist will perform ultrasound-guided placement of a jugular venous catheter to allow insertion of a Swan-Ganz catheter and collection of venous blood gases for assessment of mixed venous oxygen saturation (SvO₂) and Haemoglobin. In addition, a radial artery catheter will be placed for arterial blood gas sampling to determine arterial oxygen saturation (SaO₂).

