4.3 Premature discontinuation of study

Participants may voluntarily discontinue from study treatment and/or prematurely end their participation in the study for any reason at any time. In such case the Investigator must make a reasonable effort to contact the participant (e.g. via telephone and/or e-mail) in order to document the primary reason for this decision.

The Investigator may also decide at any time during the course of the study, to temporarily interrupt or permanently discontinue the study treatment if it is deemed that continuation would be detrimental to, or not in the best interest of the participant.

Circumstances requiring premature treatment interruption or discontinuation of the study, include but are not limited to:

- Study participation while in violation of the inclusion and/or exclusion criteria
- *If applicable:* Pregnancy
- *If applicable:* Intention of becoming pregnant

In any such case of early study termination and/or treatment interruption/discontinuation, the treating physician will continue to closely monitor the participant's condition and ensure adequate

medical care and follow-up. It is recommended that follow-up information will be collected as follows:

No study visit will take place, however, standard clinical follow-up will proceed as previously scheduled.

For participants whose status is unclear because they fail to appear for study visits without stating an intention to discontinue or withdraw, the Investigator must make every effort to demonstrate "due diligence" by documenting in the source documents which steps have been taken to contact the participant to clarify their willingness and ability to continue their participation in the study (e.g. dates of telephone calls).

A participant should not be considered lost to follow-up until due diligence has been completed.

5 Safety reporting

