5.1 Definitions

5.1.1 Adverse Event (AE)

An AE is any untoward medical occurrence in a patient or participant during an experiment, and which does not necessarily have a causal relationship with the treatment or intervention.

An AE can therefore be any unfavourable and unintended sign (including an abnormal laboratory finding), symptom or disease temporally associated with the use of a product or intervention, whether or not considered related. Any worsening (i.e., any clinically significant adverse change in the frequency or intensity of a pre-existing condition) should be considered an AE.

Events that occur between the screening visit and the study visit will not be recorded as AEs or SAEs. Eligibility criteria will be reassessed at the study visit.

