PCWP will be measured as the average end-expiratory value over four consecutive respiratory cycles, following a 10-second period to allow for hemodynamic stabilization. By comparing each PCWP value to the average of the PCWP measured during the pacing-off periods immediately before and after the pacing-on phase, we aim to minimize the impact of spontaneous hemodynamic variability and carry-over effects (41). The heart rate associated with the greatest reduction in PCWP will be repeated as the final pacing-on step, during which CO will be measured by collecting arterial and mixed venous blood samples (direct Fick principle). If two pacing rates result in an equal reduction in PCWP, the lower pacing rate will be selected. If no reduction in PCWP is observed with accelerated pacing, the heart rate corresponding to the smallest increase in PCWP will be selected for the final pacing-on period instead. In this final step, PCWP will be measured again to verify that it remains consistent with the initial PCWP at the same pacing rate. Only the initial PCWP measurement at the optimal pacing rate will be used in our analyses assessing changes in PCWP compared to the intrinsic heart rate.

The pacing rate will never exceed the APMHR, calculated based on Takana's equation (42). If this threshold would be reached, the protocol will be stopped at the pacing step prior to exceeding the APMHR, only followed by the final pacing step in which the pacing rate associated with the greatest reduction in PCWP is repeated.

16 APPENDIX 4: Detailed description of the study protocol during exercise

The following section provides a stepwise description of the pacing protocol performed during exercise (Figure 4):

- Pacing-off:
 - Measurement of SWV
 - PCWP measurement after 10s of cycling
- Pacing-on:
 - Set the pacemaker to DDD mode with a lower rate of **10** bpm above the intrinsic heart rate, rounded to the closest decimal and with dynamic AV-delay settings
 - Evaluate mitral inflow pattern on echocardiography for evidence of E-wave truncation; if truncation is observed, the AV-delay will be adapted accordingly.
 - Non-invasive measurement of BP
 - Measurement of SWV
 - 10s after the last change in pacemaker settings: PCWP measurement
- Pacing-off:
 - Reprogram the pacemaker to back-up mode
 - Measurement of SWV
 - 10 seconds after pacemaker reprogramming: PCWP measurement
- Pacing-on:

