 - Set the pacemaker to DDD mode with a lower rate of **30** bpm above the intrinsic heart rate, rounded to closest decimal and with dynamic AV-delay settings

- Evaluate mitral inflow pattern on echocardiography for evidence of E-wave truncation; if truncation is observed, the AV-delay will be adapted accordingly.
- Non-invasive measurement of BP
- Measurement of SWV
- 10s after the last change in pacemaker settings: PCWP measurement
- Pacing-off:
 - Reprogram the pacemaker to back-up mode
 - Measurement of SWV
 - 10 seconds after pacemaker reprogramming: PCWP measurement
- Pacing-on:
 - Set the pacemaker to DDD mode with a lower rate of **50** bpm above the intrinsic heart rate, rounded to the closest decimal and with dynamic AV-delay settings
 - Evaluate mitral inflow pattern on echocardiography for evidence of E-wave truncation; if truncation is observed, the AV-delay will be reduced accordingly.
 - Non-invasive measurement of BP
 - Measurement of SWV
 - 10s after the last change in pacemaker settings: PCWP measurement
- Pacing-off:
 - Reprogram the pacemaker to back-up mode
 - Measurement of SWV
 - 10 seconds after pacemaker reprogramming: PCWP measurement
 - After PCWP measurement: collection of arterial and mixed venous blood samples
- Pacing-on
 - Set the pacemaker to DDD mode with a lower rate corresponding to previously determined rate with the greatest reduction in PCWP
 - 10 seconds after pacemaker reprogramming: PCWP measurement
 - After 4 respiratory cycles: collection of arterial and mixed venous blood samples
- Pacing-off

The pacing-off periods will be set at 20 bpm below the intrinsic heart rate, unlike the fixed 40 bpm backup pacing mode used at rest. During exercise, no optimal AV delay will be determined; instead, dynamic AV delay regulation will be applied and subsequently verified to ensure no truncation occurs. If truncation is detected, the AV delay will be adjusted accordingly. Additionally, blood pressure will be measured noninvasively three times

Following this protocol at 10 Watts, the procedure will be identically repeated at 25 Watts. All other procedures and considerations are identical to those described for the protocol at rest.

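### Exclusion 8g (PCWP > 40 mmHg during exercise) cannot work as an entry criterion, and the plan gives no single instruction for such a reading during the test

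*Combined protocol and SAP*

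**What the plan says.** - **Criterion.** Section 3.2 lists, under contraindications to CPET, item 8g: "Severely elevated PCWP (> 40 mmHg) during exercise". Anyone meeting an exclusion criterion is not to be enrolled and "will be documented as a screen failure via applicable log forms in Investigator Site File".
- **Endpoint.** The exercise part of section 2.2 is the change in PCWP at each pacing rate "compared to PCWP at the intrinsic heart rate during exercise (cycle ergometry at 10 and 25 Watts").
- **When eligibility is checked.** Section 5.1.1 states: "Eligibility criteria will be reassessed at the study visit". Section 4.2.2 puts that check before the catheters are placed: "If all eligibility criteria are still met, the iCPET will proceed". Its list of screening data contains no exercise haemodynamics.
- **Violation found later.** Section 4.3 names, among circumstances requiring interruption or discontinuation, "Study participation while in violation of the inclusion and/or exclusion criteria".
- **Reporting.** Section 5.1.5 repeats the seven items 8a to 8g as adverse events of special interest during the invasive test, on the timelines for serious events. It attaches no stop.
- **Exercise procedure.** In Appendix 4 the first PCWP is read after 10 seconds of cycling at 10 W. Then: "Following this protocol at 10 Watts, the procedure will be identically repeated at 25 Watts". The only numeric stop in the two appendices is the limit on pacing rate set by age-predicted maximal heart rate. It is written in Appendix 3 and carried over to exercise: "If this threshold would be reached, the protocol will be stopped at the pacing step prior to exceeding the APMHR".
- **Data status.** Section 4.2.1 allows use of data collected before withdrawal of consent. Section 6 defines no analysis set and defers further detail to a SAP still to be written.

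**The concern.** An entry criterion should be known before entry. This one is defined on an outcome variable and normally becomes known only after the participant has consented, been catheterised, completed the whole resting pacing protocol and started cycling. Staff who see 41 mmHg at 10 W then have no single rule for two decisions: whether to stop the exercise, and whether the participant still counts.

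Both matter. A participant taken on to 25 W does so after meeting what the plan itself calls a contraindication to the test. A participant handled as a screen failure may have the resting data and any completed exercise pairs set aside, and is among those with the highest exercise filling pressure, the group the intervention is meant to help. Two sites could reasonably act differently on the same reading.

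**Working it through.** **Step 1: can 8g be applied at entry?** In order, the plan has screening (no exercise PCWP), scheduling of the test once all criteria are met, a recheck at the study visit before catheter placement, the resting pacing protocol, and then the first exercise PCWP. Unless an earlier invasive exercise test exists, which the plan does not require, 8g is unknown at every eligibility check.

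**Step 2: what happens at a reading above 40 mmHg?**

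| Place | Instruction | Stops exercise? | Settles data status? |
|---|---|---|---|
| 3.2 | not enrolled; screen failure | not written for an enrolled participant | implies the person does not count |
| 4.3 | interruption or discontinuation for an eligibility violation | yes, if the reading is a violation | no |
| 4.2.1 | data before consent withdrawal usable | no | only for withdrawal |
| 5.1.5 | report | no | no |
| 5.3.2 | physician monitoring; backup pacing on haemodynamic compromise | gives no PCWP value | no |
| Appendix 4 | repeat at 25 W | no PCWP condition | no |

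**Step 3: how likely is the situation?** The documents give no rate p, so it is assumed. P(at least one of 20) = 1 − (1 − p)^20:
- p = 2%: 33%
- p = 5%: 64%
- p = 10%: 88%
- p = 20%: 99%

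**Step 4: effect on power and the estimate (illustrative).** Plan's own figures (6.1): mean difference −2 mmHg, SD 2.5 mmHg (taken as the SD of the paired difference), two-sided 5%, 80% power, 16 needed, 20 enrolled. The paired t-test (noncentral t) needs 15 (power 0.821). It gives 0.848 at n = 16 and 0.924 at n = 20. Dividing 15 by the Wilcoxon efficiency 0.955 gives 15.7, so 16. The plan's figure is reproduced, and 16/(1 − 0.20) = 20.

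Suppose crossers on a pacing-off reading were dropped. With share p, z = z(1 − p), λ = φ(z)/(1 − p), and ρ the assumed correlation of the change with pacing-off PCWP:

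mean = −2 − ρ × 2.5 × λ; SD = 2.5 × √(1 − ρ²λ(λ + z)).

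For p = 20%, ρ = −0.5: z = 0.842, λ = 0.350, mean = −2 + 0.5 × 2.5 × 0.350 = −1.56, SD = 2.37, power at n = 16 is 0.695.

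| ρ | p = 5% (n = 19) | p = 10% (n = 18) | p = 20% (n = 16) |
|---|---|---|---|
| 0 | −2.00, power 0.909 | −2.00, 0.892 | −2.00, 0.848 |
| −0.3 | −1.92, 0.891 | −1.85, 0.852 | −1.74, 0.755 |
| −0.5 | −1.86, 0.883 | −1.76, 0.830 | −1.56, 0.695 |

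Dropping on a paced reading instead (pacing-off mean 28, 31 or 34 mmHg and SD 7, both assumed) moves the mean by at most about 0.2 mmHg, in a direction that depends on ρ.

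**Step 5: does a stopping rule give a less biased estimate?** Not by itself. I simulated stops at any 10 W reading and at the 25 W pacing-off or first paced reading. Assumptions: pacing-off mean 34 mmHg and SD 7 at both workloads, correlation 0.85 between them, ρ = −0.5. About 27% have no usable 25 W pair, and the complete-case change at 25 W is about −1.5 mmHg. That is no better than −1.56 in the table.

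**The case against.** The strongest reply is that the plan never says anyone is dropped on their outcome. Section 3.2 is an entry gate and is not written for someone already enrolled and paced. Section 4.3 stops procedures and is silent on data. The one sentence on data status, in 4.2.1, points to retention, although it is written for consent withdrawal. The repetition of 8a to 8g in 5.1.5 suggests that the authors expected such participants to stay in the study and be reported, so 8g is probably a test-safety item that was also placed among the exclusions. All of this stands. A reader might infer that crossers' data will be deleted, and the documents do not support that.

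The reply also notes that removal for a violation and continuation to 25 W are alternative readings: if the reading is a violation, 4.3 already requires interruption or discontinuation. That is right, and the two harms cannot both apply to one participant. But it restates the problem: the plan does not say which reading governs.

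It can also be said that safety is covered by investigator discretion (4.3), physician monitoring and backup pacing on compromise (5.3.2). These safeguards are real, so it would be wrong to say that the plan has no safety stop. None of them names a PCWP value or ends exercise because of one. Figure 4 is not shown, and a stop drawn there cannot be excluded. A later SAP can settle the data status but cannot supply a bedside stop.

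**Conclusion.** The point holds as an inconsistency that should be corrected before enrolment. Item 8g cannot screen anyone without an earlier invasive exercise test, and a reading above 40 mmHg during the test meets three instructions that do not agree: treat as a violation, report, or carry on to 25 W.

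The size of any bias cannot be determined from the documents. The illustration rests on assumed crossing rates and correlations. If the effect is unrelated to pacing-off PCWP, dropping on a pacing-off reading gives no bias. At about 5% crossing all effects are small, and power falls below 80% only near 20% crossing with a nonzero correlation. A reader might infer that the primary result is materially biased, or that a stopping rule would remove such bias; neither is shown. The case rests on participant safety and on consistent handling across two sites. Confidence is medium, chiefly because Figure 4 is not shown and the SAP is still to come.

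**What to change.** 1. **Section 3.2:** limit 8g to a value known before the study test.
2. **Appendix 4:** make PCWP > 40 mmHg (four-cycle average, pacing on or off) an on-test stopping criterion, checked at each step and before starting 25 W, and record the reading that triggered the stop.
3. **Section 6 or the SAP:** state that such a participant stays enrolled, is not a screen failure, and contributes all pairs obtained before the stop. Because 2.2 averages the pacing-off readings before and after each step, say also how a step stopped on its paced reading is treated.
4. **Reporting:** give the number stopped per workload and the triggering reading (off or on), and note that the 25 W results then describe participants who did not cross.

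A sensitivity analysis for 25 W based on the first 10 W pacing-off reading, which every participant who starts exercise should have, is optional.

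**Cost:** a few sentences and no added measurement, since PCWP is already read at every step. Participants stopped at 10 W give no 25 W data: 0.05 × 20 = 1 to 0.20 × 20 = 4 participants if 5% to 20% cross there. A stop at the first 10 W reading leaves no 10 W pair either, and stops at 25 W lose further pairs. The planned 20 need not change unless stops and other dropout together exceed 4 participants (20%).
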